TRIAL PROTOCOL

ABBRUPT

A randomised controlled trial to investigate clinical and cost effectiveness of Amiodarone vs Beta Blockade for new onset atrial fibRillation in icU - a Pragmatic sTudy

This protocol has regard for the HRA guidance and is compliant with the SPIRIT guidelines (2013)

Version Number: 4.0

Version Date: 20th January 2025

PROTOCOL DEVELOPMENT

Protocol amendments

The following amendments and/or administrative changes have been made to this protocol since the implementation of the first approved version. Amendments to the protocol will be made in collaboration with the TMG and the Sponsor will decide if the amendment is substantial or non-substantial. Amendments will be communicated to MHRA &/or REC as appropriate by completion of the amendment tool and approvals will be emailed to Trust's R&D departments. The amendment history will be tracked within the protocol using the table below.

Amendment number	Date of amendment	Protocol version number	Type of amendment	Summary of amendment
1	16 th May 2024	2.0	Substantial	Correction of minor typographical errors and administrative updates throughout. Change of wording to magnesium exclusion criteria. Amalgamation of two inclusion criteria. Addition of sepsis as an expected SAE. Removal of amiodarone loading dose. Removal of list of beta blockers. Remove decreased libido from list of AEs. Removal of NHS number and Chi number. Removal of National Opt-Out register. Removal of EQ-5D-5L at baseline in Health Economics analysis.
2	30 th July 2024	3.0	Substantial	Correction of minor typographical errors and administrative updates throughout. Addition of PPI members to TMG Addition of ACCPs to Section 4.3: confirmation of eligibility Change of wording to Section 7.7.2: packaging and labelling

				Interim change of CI to [name]
				Amendments to inclusion/exclusion criteria:
				I. Add definition of NOAF
				II. Amended wording to inclusion criteria
				III. remove exclusion 'in receipt of amiodarone or beta blocker within previous 24 hours'
3	20 th January 2025	4.0	Substantial	IV. remove 'other thoracic surgery that ingresses the thorax
				V. Remove 'A serum magnesium value below the index hospital laboratories lower limit of normal'
				Remove paper EQ5D
				Add streamlined eligibility and randomisation process
				Removal of sub-study
				Remove SmPCs and refer to RSI instead

Funding and support in kind	

DSUR	Development Safety Update Report
GCP	Good Clinical Practice
HR	Heart Rate
HRA	Health Research Authority
НТА	Health Technology Assessment Programme
ICF	Informed Consent Form
ICU	Intensive Care Unit
ISF	Investigator Site File
IV	Intravenous
ITT	Intention to Treat

Myocardial infarction
National Health Service
Mean Arterial Pressure
National Institute for Health and Care Excellence
National Institute for Health and Care Research
New-onset atrial fibrillation
Principal Investigator
Patient Information Sheet
Personal Social Services
Quality-adjusted life year
Research Ethics Committee
University of Birmingham Research Governance team
Reference Safety Information
Serious Adverse Event
Statistical Analysis Plan
Serious Adverse Reaction
Summary of Product Characteristics
Suspected Unexpected Serious Adverse Reaction
Trial Master File
Trial Management Group
Trial Steering Committee
University of Birmingham
Women of child-bearing age

TRIAL SUMMARY

Title

A randomised controlled trial to investigate the clinical and cost effectiveness of Amiodarone vs Beta Blockade for new onset atrial fibRillation in icU - a Pragmatic sTudy.

Objectives

To conduct a multi-centre, randomised trial comparing two commonly used treatments (beta blocker and amiodarone) for new onset Atrial Fibrillation (NOAF) in intensive care.

To perform clinical and full economic evaluation to compare treatment with beta blockers and amiodarone.

Trial design

Open-label interventional multi-centre two-arm randomised controlled trial with internal pilot and economic evaluation.

Patient population and sample size

Patients (≥16 years) requiring a high level of care with NOAF or a new episode of AF within this acute admission for which therapeutic intervention with either beta blockers or amiodarone is planned by the clinical team. In total, 2560 patients (1280 per arm) will be randomised.

Setting

Critical care units in NHS Trusts/ Health Boards within the UK

Eligibility criteria

Inclusion criteria

- Adult Patients (age ≥16 years)
- Monitored in an area of higher care with the ability to deliver the interventions
- Onset of NOAF or a new episode of AF during the acute illness (A&E, deterioration on ward, after surgery) where there is a clinical indication to treat with amiodarone or beta blockers as determined by the attending clinician/ACCP or equivalent.
- Usual electrolyte management with potassium and magnesium has taken place according to site practice

Exclusion criteria

- Treatment with anticoagulants or antiarrhythmics for the treatment of AF before the current hospital admission *anticoagulants or antiarrhythmics used for any other purpose can be included
- Current concomitant medication that are contraindicated with the intervention / comparator medications (e.g. Ciclosporin, Itaconazole, Letermovir)
- Serum Potassium of < 4 mmol ^{L-1} (measured either on Point-of-Care Testing or Laboratory)
- Patients having undergone cardiac surgery during the current hospital admission, defined as
 any surgery including lung resections, stent procedures such as percutaneous coronary
 interventions or other angioplasty procedures done on the heart muscle, valves or thoracic
 arteries including the thoracic part of the aorta
- Thyrotoxicosis
- Withdrawal of life support therapy within 24 hours
- Any other known contraindication or known sensitivity to beta-blockers or amiodarone
- Known pregnancy or patients currently known to be breast-feeding

Interventions

Intervention: Amiodarone Comparator: Beta-blockade

Both the intervention and comparator should be applied for as long as is usual in your local practice.

Outcome measures

Primary outcome

• 90-day mortality

Secondary outcomes

Clinical Outcomes:

- ICU and hospital mortality
- Rates of cardiovascular events including stroke, myocardial infarction or thromboembolism up to 90-days
- Rate of established AF by the end of ICU stay / death / Day 90

Safety outcomes:

- Number of episodes of bradycardia (HR <50 bpm) whilst in hospital and being prescribed the intervention
- Bradycardia and bradycardic arrhythmias with haemodynamic compromise requiring intervention
- Significant hypotension requiring intervention (not including temporarily stopping the trial medication) whilst in ICU
- Heart block
- Arrhythmia with haemodynamic compromise requiring intervention including DC cardioversion

Economic Outcomes:

- Cost-effectiveness of the interventions
- Health care resource use including ICU and hospital length of stay

TRIAL SCHEMA

[figure not shown]

TABLE OF CONTENTS

1	BACKGROUND AND RATIONALE	19
1.1	Background	19
1.2	Trial rationale	19
1.3	Justification for patient population	20
1.4	Justification for design	20
1.5	Justification for choice of intervention(s)	21
1.6	Justification of choice of primary outcome	21
2	AIMS AND OBJECTIVES	22
2.1	Internal pilot objectives	22
2.2	Main trial objectives	22
2.2	2.1 Clinical aims and objectives	22
2.2	2.2 Economic aims and objectives	22

1 BACKGROUND AND RATIONALE

1.1 Background

Atrial Fibrillation (AF) is a supraventricular tachyarrhythmia resulting from irregular, disorganised electrical activity and ineffective contraction of the atria (1); New Onset AF (NOAF) does not have a widely accepted definition, but for the purposes of this trial, ABBRUPT, we will define NOAF as AF during the acute illness (A&E, deterioration on ward, after surgery) where there is a clinical indication to treat with amiodarone or beta blockers as determined by the attending clinician/ACCP or equivalent. Patients having received anticoagulation or antiarrhythmics for the treatment of AF before the current hospital admission do not fall under this definition however, anticoagulants or antiarrhythmics used for any other purpose than for treating AF can be included. AF occurs in approximately 5-26% of Intensive Care Unit (ICU) patients (2,3), depending on age, sex, obesity, comorbidities and the reason for ICU admission (2). The risk of AF increases in the presence of sepsis with one systematic review reporting an incidence of 46% (4). Although AF often resolves, AF recurs in up to 18% (5) of cases and is associated with severe complications such as death, stroke or myocardial infarction (MI) in the longer-term. A 2021 review (6) reported higher mortality in hospital and during the first 90-days after ICU discharge (adjusted odds ratio 2.32, 95% CI 2.16 to 2.48; adjusted Hazard Ratio 1.46, 95% Confidence Interval 1.26 to 1.70, respectively) in patients with NOAF. Readmission rates for stroke and heart failure (adjusted cause-specific Hazard Ratio 1.47, 95% Confidence Interval 1.12 to 1.93; and adjusted cause-specific Hazard Ratio 1.28, 95% Confidence Interval 1.14 to 1.44, respectively) were also higher in patients with NOAF.

There are no prospective randomised studies comparing amiodarone with beta blockade reporting long term, clinically relevant outcomes. A retrospective analysis of the 38,159-patient MIMIC III dataset reported (7) that, compared with those who did not develop AF, there was significantly higher 90-day and hospital mortality (20.8% versus 15.3%) and beta blocker use had a protective effect (Hazard Ratio 0.59, 95% Confidence Interval 0.53–0.65, p<0.001). Amiodarone was associated with a higher mortality (Hazard Ratio1.16, 95% Confidence Interval 1.05–1.29, p=0.004). There are no information about the application of the treatment used and potential confounders, such as concomitant medications or whether amiodarone was used in patients with higher inotrope and vasopressor use.

Work by our own group (8) and others (9) has reported that the majority of intensivists use amiodarone to treat AF in the critically ill. Given the results from MIMIC and the analysis by Chean et al (8), there is a clear need to distinguish whether there is a difference in outcome in patients managed with amiodarone compared with beta blockade. ABBRUPT is a comparison of amiodarone and beta blockade to establish which management of AF is best to avoid harm and achieve optimal outcomes.

1.2 Trial rationale

The impact of developing AF in the ICU has been studied in a number of large retrospective analyses. ICU/Hospital Mortality: Several papers (10-13) have reported ICU mortality but are best summarised in 2019 systematic reviews and meta-analyses of 12 papers in NOAF only and excluding papers reporting established AF (14). There were significant differences in hospital mortality in ICU patients with NOAF compared with patients without (Odds Ratio 2.70; 95% Confidence Interval 2.43-3.00) (14), and a subgroup analysis of patients with sepsis or septic shock showed a significant association between NOAF and hospital mortality (Odds Ratio 2.32; 95% Confidence Interval 1.88-2.87) (14).

In a study of 3334 critically ill patients, NOAF was associated with increased in-hospital mortality and 1-year mortality. The mortality within the first year after being discharged from the hospital alive was 4.6% in patients with no AF, 11.6% in the patients with known AF and 26.0% in patients with NOAF

(15). A study of 1841 critically ill patients reported that there was higher post-ICU risk of death in the ICU survivors with AF (Hazard Ratio 2.2, P < 0.001) (14) compared to those without AF.

Excess mortality in patients with sepsis and septic shock: Meierhenrich reported a hospital mortality rate of 44% in those with NOAF versus 22% for those who did not in surgical ICU patients; hospital mortality was 45% for individuals with NOAF versus 16% for those without (16).

NOAF is also associated with increased morbidity. Studies report that patients with sepsis who develop NOAF have a greater risk for in-hospital stroke (2.6% versus 0.6%) (17), and subsequent hospitalisation for heart failure (11.2% versus 8.2%) compared with those who do not (18). Moreover, NOAF may not resolve; up to 18% of patients have been reported to have been discharged from ICU with persistent AF (5).

Although the prognostic significance of NOAF in ICU is established, what is not known is whether different treatment strategies can modify the associated morbidity and mortality that comes with it. Patients with AF require more vasopressor and inotropic support. Shaver (12) reported in 1770 patients, that those with AF were more likely to be treated with vasopressors or inotropes compared with patients who did not develop AF in the ICU (59.7% vs. 43.2%, p<0.001) and were treated with vasopressors for longer (1.7 \pm 1.5 days in NOAF vs. 1.0 \pm 1.3 days without AF, p<0.001). The requirement for additional vasoactive support may be a factor in adverse clinical outcomes. This is a current active area of study by our group and supported by the NIHR in the STRESS-L study (19) (NIHR EME - 14/150/85).

ICU survivorship leads to chronic ill health, morbidity and mortality. NOAF is also associated with significant on-going costs in terms of disability, care and treatments (20). ICU clinicians need to understand the best treatments to apply at the time of critical illness to optimise "good survivorship" — that is a long and healthy post-ICU recovery. In surveys from 2017 and 2021 (8,9), we have observed a trend in treatment preferences away from amiodarone towards beta blockade, but without the evidence of the benefit for either. Physicians' growing awareness of NOAF as a major determinant of longer-term ICU outcome together with a lack of evidence on how to treat it, suggests that there is now an opportunity to determine best treatment options.

ABBRUPT will investigate important clinical outcomes, but will also provide an ideal opportunity for further, separately funded, mechanistic studies.

1.3 Justification for patient population

The development of NOAF in ICU is associated with a several unwanted side effects including an increased risk of myocardial events, stroke and death in the twelve months following ICU discharge. Retrospective studies suggest that management with amiodarone (when compared with beta blockade) is associated with worse outcomes. There is however concern that these data are biased as patients who are cardiovascularly stable could have been excluded from receiving beta blockers. The ABBRUPT trial will study the widest possible population of critically ill patients in ICU as the impact of NOAF management on 90-day mortality is unknown.

1.4 Justification for design

The CAFÉ report (6) noted that beta-blockers and amiodarone appear to be similarly effective in achieving cardiovascular control, but digoxin and calcium channel blockers appear to be inferior. The majority of intensivists use amiodarone to treat AF in the critically ill (8,9) but the proportion who use beta blockade is increasing. There are no studies available to define the optimal administration route, time and dose for either of the study drugs nor are there studies demonstrating that one particular beta blocker is superior to another. With the wide range of available drugs, route of administration

(IV or oral) and duration of treatments, a robust clinical trial is required to determine evidence based practice for intensities using amiodarone and/or beta-blockers for treating NOAF.

A randomised study such as ABBRUPT is necessary to inform ICU clinicians whether amiodarone or beta blockade is better to avoid 90-day mortality for the drug management of NOAF in ICU.

1.5 Justification for choice of intervention(s)

Despite being used as an anti-arrhythmic agent since the 1970s, amiodarone is relatively understudied in the ICU, and there are only few studies that have measured either beneficial or harmful associations with its use. An extensive systematic literature review was not able to define the superiority of amiodarone or beta-blockers as anti-arrhythmic agents for rhythm or rate control in NOAF (21). In addition, there are very few laboratory studies on the effects of amiodarone. However, in one animal study (22), amiodarone affected both phagocytic function and cell-mediated immunity possibly through the inhibition of phospholipase C. This may represent an immunomodulatory effect. The clinical impact of such immunomodulation on morbidity and mortality is unclear.

Beta blockers, on the other hand, have been widely studied in a variety of animal and cell studies. Beta blockers may have effects in the critically ill beyond cardioversion and heart rate (HR) control which are currently under investigation by our group (19). Clinically, HR control with beta blockers have been associated with improved outcomes in a variety of conditions including myocarditis, liver failure, multiple myeloma, traumatic brain injury, trauma, septic shock and burns (reviewed (23)). However, a meta-analysis of the use of beta blockers peri-operatively (24) reported that beta blockade prevented non-fatal MI but increased the risk of stroke, death, hypotension, and bradycardia. None of these studies has been replicated with amiodarone which has a wide variety of actions including some ability to block beta receptors. The potential side-effects of amiodarone are hypotension during infusion and an increased risk of chronic interstitial pneumonitis and organizing pneumonia (25) the impact of which remain unknown.

1.6 Justification of choice of primary outcome

NOAF in the ICU is associated with short-term and long-term mortality. Studies (6) have found that the rates of conversion to sinus rhythm are similar between amiodarone and beta blockade, but there is a possibility of an increase in long-term morbidity and mortality associated with either of the study interventions. The primary outcome in ABBRUPT is to determine if there is a difference in 90-day mortality rates between amiodarone and beta blockade.

2 AIMS AND OBJECTIVES

2.1 Internal pilot objectives

The success of the internal pilot will be based upon the following factors: patient recruitment, commencement of an alternative treatment, study drop-out and data completeness.

The number of patients to be recruited in the 9-month internal pilot will be 250 from at least 15 recruiting sites, assuming staggered site opening and for each site to recruit on average 2 patients per month. The decision for the trial to continue will be decided by pre-defined progression criteria below:

- Green: Recruitment rate 100%, alternative treatment rate <5%, drop-out rate <5%, data completeness ≥90%. If all criteria are met; continue the trial with protocol unchanged.
- Amber: Recruitment rate 75-99%, alternative treatment rate 5-10%, drop-out rate 5-10%, data completeness 80-89%. If one or more of our amber criteria are met, then the study will need review to see what changes (if any) could be made to improve whichever criteria are not at the "green" level.
- Red: Recruitment rate <75%, alternative treatment rate >10%, drop-out rate >10%, data completeness <80%. If one or more of these criteria are met, we will discuss with the Trial Steering Committee (TSC) and the funder regarding feasibility of the study continuing.

Length of internal pilot phase: 9 months

Progression criteria	Red	Amber	Green
% Threshold	<75%	75-99%	≥100%
Alternative treatment rate	>10%	5-10%	<5%
Drop-out rate	>10%	5-10%	<5%
Data completeness	<80%	80-89%	≥90%
Recruitment rate/site/month	<1.5	1.5-1.9	2
Number of sites opened	<12	12-14	15
Total number of patients recruited	<172	172-249	250

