8 OUTCOME MEASURES

8.1 Pilot Outcomes

- 250 patients recruited from at least 15 sites
- Alternative treatment to randomised arm of <5%
- Drop-out rate of <5%
- ≥90% data completeness of the primary outcome

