16 STATISTICAL CONSIDERATIONS

16.1 Sample size

Sample size calculation is based on a time-to-event superiority analysis. Literature (8) suggests that 90-day mortality in patients with NOAF was approximately 20%. A 5% absolute difference in mortality is considered a 'meaningful clinically important difference [MCID]' which equates to a hazard ratio of approximately 0.73. Using 90% power and a 2-sided alpha of 0.05 to detect a hazard ratio of 0.73 with event rate of 20% (or survival rate of 80%), a total of 426 events will be required. The enrolment of approximately 2430 patients would provide the required number of primary outcome events. Allowing for a 5% non-evaluable rate, a total of 2560 patients (1280 per group) will need to be recruited (rounded to nearest 10). We have allowed for a slightly higher non-evaluable rate as this study is recruiting critically ill patients undergoing an acute deterioration during their care.

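### The pilot progression table sets the red/amber cut for total recruitment at 172 patients, which is 68.8% of the 250 target and not the stated 75%

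*Protocol*

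**What the plan says.** Section 2.1 fixes the size of the pilot: "The number of patients to be recruited in the 9-month internal pilot will be 250 from at least 15 recruiting sites". It then gives three progression bands, first in text and then in a table.

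The text defines the lowest band as "Red: Recruitment rate <75%, alternative treatment rate >10%, drop-out rate >10%, data completeness <80" (per cent). Amber is 75 to 99% recruitment and green is 100%.

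The table has four rows that bear on recruitment, each listed in the order red, amber, green:

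- percentage: "Threshold <75% 75-99% ≥100" (per cent)
- rate: "Recruitment rate/site/month <1.5 1.5-1.9 2"
- sites: "Number of sites opened <12 12-14 15"
- total: "Total number of patients recruited <172 172-249 250"

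Section 2.1 also says how the criteria combine. Green needs every criterion at green level. Amber or red applies as soon as at least one criterion falls in that band. The actions differ: amber leads to a review of what might be changed, and red leads to a discussion with the Trial Steering Committee and the funder about whether the trial is still feasible.

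**The concern.** The percentage row and the total row describe the same quantity, recruitment against a target of 250, so their boundaries should coincide. At the green end they do: 100% is 250. At the red/amber end they do not: 75% of 250 is well above 172.

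These criteria are fixed in advance so that the pilot result can be read off without argument. If the total falls between the two boundaries, someone reading the count row records amber and someone reading the percentage records red. The disagreement would come to light only when the decision is due, with the result already known.

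**Working it through.** **Inputs (all from section 2.1).** Target 250 patients; 9 months; at least 15 sites; 2 patients per site per month; red/amber boundary 75% (text and table); red/amber boundary 172 (count row); rate cut 1.5; site cut 12.

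**1. The plan's own figure.** Boundary = percentage × target = 0.75 × 250 = 187.5, so the smallest total that is not red is 188. The table gives 172, and 172 / 250 = 0.688, or 68.8%. The stated figure is not reproduced. It is 188 − 172 = 16 patients too low, or 75 − 68.8 = 6.2 percentage points.

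**2. Other routes to 172.**

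| Route | Calculation | Result |
|---|---|---|
| 75% of the full capacity of 15 sites | 0.75 × (15 × 2 × 9) = 0.75 × 270 | 202.5 |
| Amber site and rate minima, all sites open throughout | 12 × 1.5 × 9 | 162 |
| Site-months implied by the target, at the amber rate | (250 / 2) × 1.5 = 125 × 1.5 | 187.5 |
| The same with 12 of 15 sites | 187.5 × 0.8 | 150 |

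None gives 172. Working backwards, 172 / 0.75 = 229.3, and 0.75 × 230 = 172.5. A cut of 172 would therefore suit a target of about 230, but no such target appears in the protocol.

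**3. Which row is out of line.** The rate row follows 75% exactly: 1.5 / 2 = 0.75. The site row follows it too: 0.75 × 15 = 11.25, so 12 is the first whole number that qualifies (11 / 15 = 73.3% would not). Only the total row departs from 75%.

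**4. Totals with two classifications.** These run from 172 (68.8%) to 187 (187 / 250 = 74.8%). That is 187 − 172 + 1 = 16 totals. All are below 75%, hence red by percentage, and all lie in 172 to 249, hence amber by count.

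**The case against.** The best reply is that the section already resolves the conflict. One red criterion is enough for red, and a total of 172 to 187 meets the red recruitment criterion in the text, so the outcome is red whatever the count row shows. Moreover, red does not stop the trial. It opens a discussion with the steering committee and the funder, while amber opens a review. On this view a wrong cell changes who takes part in the conversation, for 16 possible totals, and nothing else.

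Much of this stands. It limits the consequence, and it is a reason to leave the combination rule alone. It does not make the cell right. A reader who goes to the count row, the most direct place to look up a recruitment total, will find amber.

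One could also argue that the 75% refers to the rate per site and that the total is a separate criterion with its own cut. The table does not help that reading. It places 250 under 100% and 172 at the 75% boundary, and it gives no other basis for 172.

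A reader might go further and infer that the pilot target cannot be reached, because 15 sites at 2 per month for 9 months give only 270 before any staggered opening. The documents do not support this: 15 is a minimum, and no opening schedule is given. Nor is it an error that 12 sites at 1.5 per month yield 162, a red total. Separate criteria applied jointly can behave that way.

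**Conclusion.** The red/amber cut for total recruitment is wrong as written. It stands at 68.8% of target where the text and the percentage row say 75%, and 16 totals receive two classifications. This rests on reading the percentage row as recruitment against the 250 target, which its match with the text supports, and on using unrounded percentages. If percentages are rounded to whole numbers, 187 (74.8%) becomes 75% and 15 totals remain in conflict. The effect is confined to the pilot decision; sample size, primary analysis and final inference are untouched.

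A reader might also set the green level in section 8.1, "≥90% data completeness of the primary outcome", against section 16.1, "Allowing for a 5% non-evaluable rate", and conclude that green tolerates twice the planned loss and so endangers power. That does not hold as an error:

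- No figure in the completeness row is miscalculated.
- The closer counterpart of the 5% allowance is the drop-out criterion. Its green level is below 5%, and green needs every criterion met.
- Section 16.6 keeps patients with incomplete follow-up in the analysis and censors them, so they are not lost outright.
- Even if a full 10% contributed no events, the cost would be small. With the mean event rate of 17.5% (20% and 15%), 2560 × 0.95 × 0.175 = 425.6 events gives 90.1% power at a hazard ratio of 0.73; 2560 × 0.90 × 0.175 = 403.2 events gives 88.5%.

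**What to change.** Change the total-recruited row to red below 188, amber 188 to 249, green 250 or more. This brings it into line with the text, the percentage row, the rate row and the site row, and nothing else need move.

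If 172 was the intended cut, restate the recruitment percentage as 69% in both the text and the table. Because 172 / 250 is 68.8%, say that the percentage is rounded; otherwise a total of exactly 172 would still be below 69%. This route has a side effect: the rate and site rows follow 75%, and at 69% they would correspond to 0.69 × 2 = 1.38 per month and 0.69 × 15 = 10.35 sites, so the sponsor would need to say whether they stay.

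In either case keep the present rule that one criterion in a band is enough to trigger it. A rule that total recruitment decides when rows disagree would let good recruitment override a red drop-out or alternative-treatment result.

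The cost is a small table edit agreed with the Trial Steering Committee and the funder, with no effect on patients, data collection or the main sample size.

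### Internal pilot: the Red/Amber boundary for total recruitment is printed as 172, which is 68.8% of the 250 target, while the same section sets the boundary at 75% (188 patients)

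*Protocol*

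**What the plan says.** Protocol section 2.1 fixes the pilot target: "The number of patients to be recruited in the 9-month internal pilot will be 250 from at least 15 recruiting sites". Section 8.1 repeats it as "250 patients recruited from at least 15 sites", so 250 is not an isolated misprint.

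Section 2.1 then gives the progression criteria in two forms.

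- **Bullets.** Red is "Red: Recruitment rate <75%, alternative treatment rate >10%, drop-out rate >10%, data completeness <80" and Amber is "Amber: Recruitment rate 75-99%, alternative treatment rate 5-10%, drop-out rate 5-10%, data completeness 80-89". Green is a recruitment rate of 100%.
- **Table.** The percentage row reads "Threshold <75% 75-99% ≥100". Three recruitment rows follow in the same Red, Amber and Green columns: "Recruitment rate/site/month <1.5 1.5-1.9 2", "Number of sites opened <12 12-14 15" and "Total number of patients recruited <172 172-249 250".

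The consequences also stand in section 2.1. Green requires every criterion to be met. One Amber criterion is enough to trigger a review of what might be changed. One Red criterion is enough to take the feasibility of continuing to the Trial Steering Committee (TSC) and the funder.

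**The concern.** The total-recruitment row does not follow the percentage rule that heads its own columns. A pilot that ends with between 172 and 187 patients falls below 75% of target, which is Red, yet lies inside the printed Amber range for the count. Someone who reads only the count row would record Amber and hold a review; someone who reads the percentage would go to the TSC and the funder.

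The criteria are presented as pre-defined. Their purpose is that the classification is settled before the total is known. With two boundaries in print, a choice between them is left open until afterwards, and the count is the more lenient one.

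**Working it through.** **Inputs (Protocol section 2.1):** target 250 patients in 9 months; Red/Amber boundary 75%; 2 patients per site per month at target and 1.5 at the boundary; 15 sites at target and 12 at the boundary; printed boundary for the total, 172.

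**1. Can the printed 172 be reproduced from these figures?**

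- Percentage rule: 0.75 × 250 = 187.5. Not 172.
- Per-site rate on the exposure that the target implies: 250 / 2 = 125 site-months; 125 × 1.5 = 187.5. Not 172.
- 12 sites, no staggering, 1.5 per month: 12 × 9 × 1.5 = 162. Not 172.
- Target scaled by both boundary rows: 250 × (12/15) × (1.5/2) = 150. Not 172.
- Target scaled by sites only: 250 × 12/15 = 200. Not 172.
- 15 sites, no staggering, at target rate: 15 × 9 × 2 = 270; 75% of that is 202.5. Not 172.

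Section 2.1 assumes staggered opening but gives no schedule, so some were assumed. Fifteen sites opening two a month give 2 + 4 + 6 + 8 + 10 + 12 + 14 + 15 + 15 = 86 site-months, and 86 × 2 = 172. Fifteen sites opening four a month give 4 + 8 + 12 + 6 × 15 = 114 site-months, and 114 × 1.5 = 171. Neither schedule is in the Protocol, and at the full rate of 2 they yield 172 and 228 patients, not 250.

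**2. Where does the 75% boundary fall?**

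| Total | Share of 250 | By percentage | By printed count |
|---|---|---|---|
| 171 | 68.4% | Red | Red |
| 172 | 68.8% | Red | Amber |
| 187 | 74.8% | Red | Amber |
| 188 | 75.2% | Amber | Amber |

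The two rules disagree for 172 to 187 inclusive: 187 − 172 + 1 = 16 totals.

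**3. Do the other recruitment rows follow 75%?**

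- Rate: 1.5 / 2 = 75% exactly.
- Sites: 0.75 × 15 = 11.25. Eleven sites are 73.3% and twelve are 80%, so 12 is the first whole number at or above 75%.

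Of the three recruitment rows, only the total departs from the rule.

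**4. When would the lax count change the outcome?** On the planned 125 site-months, 172 patients are 172/125 = 1.38 per site per month and 187 are 187/125 = 1.496. Both are below 1.5, so the rate row would already show Red. The rate reaches 1.5 only if exposure falls short of plan: at or below 172/1.5 = 114.7 site-months for 172 patients, or 187/1.5 = 124.7 for 187. With the assumed 114 site-months above, 172 patients give 1.51 per site per month. The rate and count rows would both show Amber at 68.8% of target, and only the percentage would show Red.

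**The case against.** The strongest reply is that the section settles the conflict itself. One Red criterion suffices for Red, so a total below 75% goes to the TSC and the funder whatever the count row says. An Amber review and a Red discussion can also both take place. A reader might infer an operational deadlock; the section does not support that. What remains is that the printed Amber range is wrong under the stated rule, and that nothing tells the reader of that row to look elsewhere.

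Second, the bullets speak of a recruitment rate, and the table has a per-site monthly rate row that fits 75% exactly. On that reading the bullets do not govern the total. This has some force, since the percentage row does not say what it is a percentage of. But that row heads the columns in which the total stands, and the per-site boundary applied to the 125 implied site-months leads to 187.5 again.

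Third, on planned exposure the rate row would already give Red for every total in the disputed range. That is correct and narrows the practical effect to a pilot whose site-months fall short of plan.

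Three stronger readings do not hold:

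- That this is a faulty stopping rule. Red leads to a discussion, not to a stop.
- That 172 cannot be derived at all. Some assumed opening schedules come to 171 or 172, so the supportable statement is that the Protocol gives no basis for it.
- That 172 is left over from a smaller target. It is true that 172/0.75 = 229.3, but the document mentions no such target.

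**Conclusion.** The point holds as an internal contradiction in the pilot progression criteria. The printed boundary of 172 is 68.8% of target; the stated boundary of 75% is 187.5, so Amber should start at 188. The printed count is too low by 188 − 172 = 16 patients.

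This rests on reading the percentage row as applying to the total, which is the natural reading of the table and agrees with the per-site row on the implied site-months.

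The consequence is limited to which progression category a shortfall receives, and so to whether the TSC and the funder must be brought in. The main sample size and the primary analysis are untouched. The Protocol does not say whether the pilot has been completed.

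**What to change.** In the progression table of section 2.1, change the total-recruitment row to Red <188, Amber 188-249, Green ≥250.

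If 172 was intended, keep 75% for the other rows, state the separate basis for 172 (for example, the opening schedule assumed), and say that this row is exempt from the percentage threshold. Lowering the general percentage to 69% would not work. Since 0.69 × 250 = 172.5, a total of 172 would still be Red, and the other rows would no longer fit: 0.69 × 2 = 1.38 rather than 1.5, and 0.69 × 15 = 10.35, hence 11 sites rather than 12.

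If the pilot decision has already been taken, record which boundary was applied.

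The cost is one table row, and the criterion becomes slightly stricter than the count now printed. No change to data collection, sample size or analysis follows.
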